7.4.5. Administration status for PRISTIQ®

Record the followings with regard to administration status for the study drug. If the posology is changed (including wash-out), please record in a separate row and the reason.

- Treatment start date
- Treatment stop date
- Daily dosage and frequency
- Reason for dose adjustment: Select one among 'planned dose increase or decrease', 'cure or improvement', 'occurrence of adverse event', 'withdrawal due to lack of efficacy' or 'other'. If 'other', record the specific reason.

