6.2 EFFECTIVENESS ENDPOINT(S)

- *[Final effectiveness evaluation]*

Final effectiveness will be evaluated at completing the administration of PRISTIQ® or at around 8 weeks treatment if PRISTIQ® has been still administered. In case of long-term use study subject, the result will be assessed after 6 months treatment of PRISTIQ®. Final effectiveness will be evaluated as 'improved', 'no change', 'worse' or 'unevaluable' based on overall patient's clinical response, CGI-I scale and investigator's judgment.

- Improved: In the case of judgment that there is the improvement of symptoms related to MDD.
- No change: In the case that there is no significant change compared to patient's status before PRISTIQ® administration.
- Worse: In the case that symptoms are getting worse compared to patient's status before PRISTIQ® administration.
- Unevaluable: In the case that the medical charts do not have adequate progress notes to make a judgment on clinical response.

- *[CGI-I scale (Clinical Global Impression – Improvement scale)]*

Clinical effectiveness will be evaluated after 8 weeks treatment (within 2 weeks of the last administration) using CGI-I scale as follows. In case of long-term use study subject, the result will be also assessed after 6 months treatment of PRISTIQ® (within 2 weeks of the last administration).

- 1. Very much improved
- 2. Much improved
- 3. Minimally improved
- 4. No change
- 5. Minimally worse
- 6. Much worse
- 7. Very much worse

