8.2 STATISTICAL ANALYSES

8.2.1 Safety Analyses

8.2.1.1 Demographic and Baseline Characteristics

Baseline characteristics for this study are defined as follows:

- Continuous measurements:
 - Age
 - Duration of disease[†]
 - Total administration period of PRISTIQ^{®‡}
 - Total dose of PRISTIQ^{®¶}

- Mean daily dose of PRISTIQ® excluding days of missed doses[§]
- Categorized measurements:
 - Age (< 30 years, \geq 30 years and \leq 49 years, \geq 50 years and \leq 69 years, \geq 70 years^{*})
 - Geriatric status (<65 years, \geq 65 years)
 - Sex (Male, Female)
 - Pregnancy (Yes, No)
 - Breast-feeding (Yes, No)
 - Duration of disease[†] (<3 months, \geq 3 months and <6 months, \geq 6 months^{*})
 - Severity of disease (Mild, Moderate, Severe)
 - Medical History (Past Disease, Present Disease/Yes, No)
 - Allergic history (Yes, No)
 - Recent past psychotropic medication (Yes, No)
 - Total administration period of PRISTIQ^{®‡} (< 4 weeks, \geq 4 weeks and <8 weeks, \geq 8 weeks and <12 weeks, \geq 12 weeks^{*})
 - Mean daily dose of PRISTIQ® excluding days of missed doses (<50 mg/day, \geq 50 mg/day and <100 mg/day, \geq 100 mg/day and \leq 200 mg/day^{*})
 - Renal disorder (Yes, No)
 - Hepatic disorder (Yes, No)
 - Long-term administration (<6 months (180 days), \geq 6 months (180 days) of total administration period of PRISTIQ®)
 - Concomitant medication (Yes, No)

[†] Duration of disease = First start date of PRISTIQ® – Diagnosis Date + 1

Subjects whose diagnosis date is included 'Unknown' are excluded from the analysis
(Footnote will be added to the relevant outputs to indicate the number of subjects collected 'Unknown')

[‡] Total administration period of PRISTIQ® = Sum of each period of administration

- In safety analysis set

Sum of each period of administration = (Last administration end date) – (First administration start date) + 1

If the medication is being continued at the completion of the study, last administration end date is replaced with last date collected in data.
- In effectiveness analysis set
 - If final effectiveness evaluation is evaluated after last administration end date,

Sum of each period of administration = (Last administration end date) – (First administration start date) + 1
 - If final effectiveness evaluation is evaluated before last administration end date or the medication is being continued at the completion of the study,

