Sum of each period of administration = (Date of final effectiveness evaluation) – (First administration start date) + 1

[¶] Total dose of PRISTIQ® = Sum of each dose of administration

: Each dose of administration = (Administration end date - Administration start date +1)*(Total daily dose)

§ Mean daily dose of PRISTIQ® excluding days of missed doses = Total dose of PRISTIQ® / Total administration period of PRISTIQ® excluding days of missed doses

* The above categories can be altered depending on the data distribution.

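### In the effectiveness set, mean daily dose divides an uncut total dose by a period cut at the evaluation date, so it is overstated when dosing is recorded after evaluation

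*SAP*

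**What the plan says.** SAP section 8.2.1.1 builds mean daily dose in three steps.

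- **Period.** The total administration period has separate rules for the safety and effectiveness sets. The effectiveness-set branch reads: "If final effectiveness evaluation is evaluated before last administration end date or the medication is being continued at the completion of the study". In that branch the period is "Sum of each period of administration = (Date of final effectiveness evaluation) – (First administration start date) + 1".
- **Total dose.** There is one rule for all sets, summed over dosing records: "Each dose of administration = (Administration end date - Administration start date +1)*(Total daily dose"). It has no evaluation cut-off.
- **Mean daily dose.** This is "Total dose of PRISTIQ® / Total administration period of PRISTIQ® excluding days of missed doses". The period without missed doses gets no formula of its own.

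For medication still being taken, the safety-set rule says that the "last administration end date is replaced with last date collected in data". No matching end date is given for the dose calculation in the effectiveness set.

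Protocol section 7.4.5 determines what the dosing records look like: "If the posology is changed (including wash-out), please record in a separate row and the reason".

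SAP section 8.2.2 then compares improvement rate across the characteristics listed in section 8.2.1.3. One of these is mean daily dose, in three categories: below 50, 50 to below 100, and 100 to 200 mg/day.

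**The concern.** The numerator and denominator cover different spans of time. When dosing is recorded after the evaluation, those days add milligrams to the total but no days to the period. Records that start after evaluation, such as a later dose change in its own row, are summed as well.

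The plan expects this situation. SAP section 6.2 has final effectiveness assessed "at around 8 weeks treatment if PRISTIQ® has been still administered", and section 8.2.1.1 writes a branch for evaluation before the last administration end date. Protocol section 7.3.3.1 also plans for at least 60 subjects treated for more than 6 months.

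The stake is the comparison of improvement rate by dose category. A subject could be placed in a higher category than the dose taken up to evaluation supports. A subject could also receive a value above 200 mg/day that fits no category and cannot be a true mean, because section 5.1 removes anyone who ever exceeded that dose.

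**Working it through.** The documents state no figure for mean daily dose, so there is nothing to reproduce. The check applies the SAP formulas to assumed dosing histories.

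**Inputs.** The formulas and category limits come from SAP sections 8.2.1.1 and 8.2.1.3. The evaluation day E, the last recorded dosing day T and the doses are assumptions, with day 1 as the first dose.

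**Formulas.**

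- As written: sum over all records of (days × daily dose), divided by (E − missed days up to E).
- Up to evaluation: the same, with every record cut at E.
- For a constant dose with no missed days, the ratio of the two is T/E.

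**Results for E = 56.**

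| Dosing history (mg/day) | As written | Up to evaluation | Category changes? |
|---|---|---|---|
| 50 to day 84 | 50×84/56 = 75.0 | 50.0 | No |
| 100 to day 84 | 100×84/56 = 150.0 | 100.0 | No |
| 75 to day 74 | 75×74/56 = 99.1 | 75.0 | No |
| 75 to day 75 | 75×75/56 = 100.4 | 75.0 | Yes |
| 200 to day 57 | 200×57/56 = 203.6 | 200.0 | Fits no category |
| 50 to day 56, then 100 to day 84 | (56×50 + 28×100)/56 = 100.0 | 2800/56 = 50.0 | Yes |
| 75 to day 84, days 29–35 missed | 77×75/49 = 117.9 | 49×75/49 = 75.0 | Yes |

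The last two rows show that T/E is not a general correction factor. T/E is 84/56 = 1.5 in both, while the actual ratios are 100.0/50.0 = 2.0 and 117.9/75.0 = 1.57.

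**Sensitivity to the evaluation day.** A constant 75 mg/day reaches 100 when T is at least 4E/3. That is day 75, 84 or 94 for E = 56, 63 or 70.

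**Long-term users.** SAP section 6.2 says: "In case of long-term use study subject, the result will be assessed after 6 months treatment of PRISTIQ". With E = 180, a constant 50 mg/day to day 210 gives 50×210/180 = 58.3 (no category change), and a constant 75 crosses only at T = 240. If the 8-week date were used for the same kind of subject, a constant 50 mg/day to day 180 would give 50×180/56 = 160.7. The SAP does not say which date applies to long-term users in the 8-week analysis.

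**Ongoing records.** No effectiveness-set end date is given for the dose, so the value is undefined. It is not shown to be inflated.

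**The case against.** The strongest reply is that the period without missed doses has no formula. Wash-outs are recorded as separate rows, so a programmer might simply count the days covered by dosing records. Numerator and denominator would then span the same days. This stands as a point about incomplete specification, and the 117.9 figure does rest on subtracting only the missed days up to evaluation. But that reading departs from the set-specific period that section 8.2.1.1 defines. It also rescues only constant doses: the subject on 50 and then 100 mg/day would get 5600/84 = 66.7, not 50.0.

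Second, the branch has two triggers. Where medication is ongoing, closing the record at the evaluation date would leave no error. That is correct, but the SAP does not write it for the dose.

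Third, exposure may be narrow. Routine observation ends at week 8, and section 5.2 removes subjects evaluated before 8 weeks of treatment. An ordinary subject therefore needs dosing recorded beyond the planned observation, by 19 to 28 days in the examples with T = 75 and T = 84. Long-term users evaluated after 6 months are affected only by dosing after that date. This stands: the frequency is unknown.

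Fourth, the category changes depend on chosen histories, and a constant 50 or 100 mg/day does not change category by day 84. A value such as 203.6 comes from a subject who already belongs in the top group. This also stands, and it limits the size of the problem. It does not make the formula right. The SAP lets categories be altered to suit the data, but new limits would not correct a wrong subject value.

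**Conclusion.** The concern holds. As written, the effectiveness-set mean daily dose is too high, relative to the mean up to evaluation, for every subject whose dosing records run past the evaluation date. This follows from the formulas and needs no assumption about the data. The size does need assumptions: with E = 56 the examples range from a factor of 57/56 = 1.02 to 2.0, and the number of subjects affected cannot be computed from the documents.

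The consequence is minor. It is confined to the mean daily dose variable in the effectiveness set and to the one comparison of improvement rate by dose category. The overall improvement rate, the CGI-I distribution, the adverse event results and the safety-set mean dose do not use it. SAP section 4 sets no hypotheses or decision rules, and Protocol section 7.7.2 makes the subgroup comparisons optional. The direction of any bias in the dose comparison is unknown.

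**What to change.** For the effectiveness set, define each dose as (the earlier of administration end date and evaluation date − administration start date + 1) × total daily dose. Ignore records that start after the evaluation, and close ongoing records at the evaluation date.

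Define the denominator explicitly as the set-specific period minus only those missed-dose days that fall on or before the evaluation date. Both parts are needed. Take 100 mg/day to day 84 with days 64–70 missed and E = 56. The rule as written gives 7700/56 = 137.5. Cutting the dose but still subtracting the later missed days gives 5600/49 = 114.3. The full fix gives 5600/56 = 100.0.

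State also whether the 8-week or the 6-month evaluation date applies to long-term users in the 8-week analysis of section 8.2.2. This is a separate gap, but the derivation cannot be programmed without it.

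The cost is one line of SAP derivation, one sentence naming the evaluation date, and the matching program change. No new data are needed and no analysis set changes.

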8.2.1.2 Adverse Events

All adverse events reported after start of administration of PRISTIQ® will be considered as on-treatment and summarised. Adverse events reported with partial dates of onset will be assumed as on-treatment, unless month/year of AE onset date is before start date of PRISTIQ®.

In the safety analysis set, the number of subjects to whom AE occurred and the number of AEs will be calculated and the incidence rate of AEs will be estimated with its 95% confidence interval.

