7. RESEARCH METHODS

7.1. Study Design

This study is open-label, non-comparative, observational, non-interventional, prospective and multi-center study in which subjects are administered PRISTIQ® as part of routine practice at Korean health care centers by accredited psychiatrists. The observation period for each subject is from initiating administration of PRISTIQ® until week 8. If administration is discontinued before week 8, observation should be done for at least 28 days from the last administration day. There will be no visit or activity mandated by this study and routine observation will be done during the above-mentioned period.

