7.4.10.1. Definition of adverse events

An AE is any untoward medical occurrence in a patient administered a medicinal product. The event need not necessarily have a causal relationship with the product treatment or usage. Examples of adverse events include but are not limited to:

- Abnormal test findings (see below for circumstances in which an abnormal test finding constitutes an AE);

- Clinically significant symptoms and signs;
- Changes in physical examination findings;
- Hypersensitivity;
- Progression/worsening of underlying disease;
- Lack of efficacy;
- Drug abuse;
- Drug dependency.

Additionally, for medicinal products, they may include the signs or symptoms resulting from:

- Drug overdose;
- Drug withdrawal;
- Drug misuse;
- Off-label use;
- Drug interactions;
- Extravasation;
- Exposure during pregnancy;
- Exposure during breast feeding;
- Medication error;
- Occupational exposure.

Abnormal test findings

The criteria for determining whether an abnormal objective test finding should be reported as an adverse event are as follows:

- Test result is associated with accompanying symptoms, and/or
- Test result requires additional diagnostic testing or medical/surgical intervention, and/or

- Test result leads to a change in study dosing or discontinuation from the study, significant additional concomitant drug treatment, or other therapy, and/or
- Test result is considered to be an adverse event by the investigator or sponsor.

Merely repeating an abnormal test, in the absence of any of the above conditions, does not constitute an adverse event. Any abnormal test result that is determined to be an error does not require reporting as an adverse event.

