7.4.10.3. Adverse events data collection

The investigator collects data on safety events as specified in Section 9 including all adverse events that occur during the observation period regardless of causal relationship to PRISTIQ®. The information on adverse events should include the specific conditions or events, duration of the events (start date and stop date), seriousness (serious or non-serious), severity, causal relationship to PRISTIQ®, actions taken, and outcome.

Check either 'yes' or 'no' in adverse event occurrence section. If 'yes', record in detail.

- Adverse event: Record the term of adverse event. If possible, specify diagnosis, not individual symptoms.
- Date of onset: Record the date of onset.
- Severity: Severity evaluation of adverse events must be done according to the following category.

1. Mild- Not causing any significant problem to the subject; Continuous medication of study drug is possible without dose adjustment.
2. Moderate- Cause a problem that does not interfere significantly with usual activities or the clinical status; Dose adjustment of study drug or other therapy is needed due to adverse event.
3. Severe- Cause a problem that interferes significantly with usual activities or the clinical status; Study drug should be stopped due to adverse event.

If the severity of an adverse event changed, the adverse event must be entered separately. Record stop date of previous severity and onset date of new severity – along with completion of all other items.

- Action: Check all relevant actions.

1) PRISTIQ®: Check the appropriate number for the adjustment of PRISTIQ® resulted from the adverse event.

1. Withdrawn (temporarily or permanently, or delayed)
2. Dose reduced
3. Dose increased
4. Dose not changed
5. Unknown
6. Not applicable

2) Others: After the onset of adverse event, the investigator should indicate other actions taken and record in detail.

1. Treatment given (please specify in concomitant medication section)
2. Others (please specify)
3. No action taken

- Seriousness: Check either ‘yes’ or ‘no’ for the question, ‘Is this case under the criteria of serious adverse event?’ If ‘yes’, record the appropriate number for the category of seriousness.

A serious adverse event is any untoward medical occurrence at any dose that:

- results in death;

- is life-threatening;
- requires inpatient hospitalization or prolongation of hospitalization;

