9.2. Reporting Period

For each patient, the safety event reporting period begins at the time of the patient's first dose of PRISTIQ®, and lasts through the end of the observation period of the study, which must include at least 28 days following the last administration of a drug under study; a report must be submitted to Pfizer Safety (or its designated representative) for any of the types of safety events listed in the table above occurring during this period. If a patient was administered a drug under study on the last day of the observation period, then the reporting period should be extended for 28 days following the end of observation.

Most often, the date of data privacy statement is the same as the date of enrollment. In some situations, there may be a lag between the dates of data privacy statement and enrollment. In these instances, if a patient provides data privacy statement but is never enrolled in the study (e.g., patient changes his/her mind about participation), the reporting period ends on the date of the decision to not enroll the patient.

If the investigator becomes aware of a SAE occurring at any time after completion of the study and s/he considers the SAE to be related to PRISTIQ®, the SAE also must be reported to Pfizer Safety.

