8.2.1.4 Adverse Events by Preferred Terms (AEs/ADRs/SAEs)

All AEs recorded in CRFs will be classified into the system organ class (SOC) and the terms of AE will be coded according to the classification of AEs in 'WHO-ART'. All AEs, except for 'Unlikely', will be considered as AE whose causal relationship to study drug cannot be excluded (hereinafter "Adverse Drug Reaction (ADR)").

- The number and percentage of AE will be presented overall and by preferred term. This will be repeated by:
 - severity
 - action
 - other action
 - seriousness
 - outcome
 - causality of adverse event to the study drug
 - other causality of adverse event to the study drug
- The number of subjects and the number of unexpected AE/ADR, Serious AE (SAE)/Serious ADR (SADR), unexpected SAE/SADR, AE/ADR will be calculated according to the preferred terms. Also, the proportion of subjects to whom AE occurred will be estimated.
- The subjects with Serious AE, unexpected AE, unexpected serious AE, AE of Geriatric, pregnant, breast-feeding, renal disorder, hepatic disorder and long term subjects will be listed for safety analyses sets.
- For subjects excluded from safety analysis set*, the number of subjects and the number of unexpected AE/ADR, Serious AE(SAE)/Serious ADR (SADR), unexpected SAE/SADR, AE/ADR will be calculated according to the preferred terms. Also, the proportion of subjects to whom AE occurred will be estimated.

* Subjects who enrolled for duplication or Subjects who have not taken PRISTIQ® or Subjects for whom adverse event status could not be established (Adverse Events status is unknown or missing in the CRF) will be excluded from this analysis.

Note: Unexpected AEs/ADRs will be classified by medical review and with reference to the local product document. Terms already included in the local product document are classified as 'expected'. All other terms that are not included in the local product document will be classified as 'unexpected'. These can't be classified without the local product document.

- For subjects excluded from safety analysis set, Serious AE, unexpected AE, unexpected serious AE will be listed for subjects excluded from safety analysis set.

- In re-examination report, SAE/SADR and unexpected AE/unexpected ADR in accordance with PT will be presented respectively according to the frequency categories of adverse events in the approved local label.

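### The SAP's on-treatment label has no end date: adverse events after the last dose are not shown separately and count against an exposure that stops at the last dose

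*SAP*

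**What the plan says.** SAP 8.2.1.2 defines which AEs are summarised: "All adverse events reported after start of administration of PRISTIQ® will be considered as on-treatment and summarised". Its rule for incomplete onset dates is also bounded only from below: "Adverse events reported with partial dates of onset will be assumed as on-treatment, unless month/year of AE onset date is before start date of PRISTIQ".

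The protocol collects events after treatment has ended. Section 7.1 says: "If administration is discontinued before week 8, observation should be done for at least 28 days from the last administration day". Section 9.2 describes a reporting period "which must include at least 28 days following the last administration of a drug under study". Section 7.3.3 adds that events recognised after the observation period are also entered on the CRF, as section 9 specifies. Section 7.4.10.3 asks for data "including all adverse events that occur during the observation period regardless of causal relationship to PRISTIQ". Among the sources of signs and symptoms that may be AEs, section 7.4.10.1 lists "Drug withdrawal".

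For the safety analysis set, SAP 8.2.1.1 computes total administration period as last administration date minus first administration date plus one. SAP 8.2.1.3 then compares the proportion of subjects with an AE across four bands of that period (under 4 weeks, 4 to under 8, 8 to under 12, and 12 or more) by chi-square or Fisher's exact test.

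**The concern.** An event that begins three weeks after the last tablet is labelled on-treatment, and nothing in SAP 8.2.1.2 to 8.2.3 distinguishes it from one that begins in the first week of treatment. Two things follow.

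First, the report cannot show which preferred terms arise on the drug and which arise after stopping, although the protocol itself names withdrawal as a source of AEs.

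Second, in the comparison by total administration period the numerator and the grouping variable use different clocks. Events count for as long as the subject is observed, while exposure stops at the last dose. Because the 28-day rule in Protocol 7.1 applies to stops before week 8, the two shortest bands hold the subjects whose required observation includes the largest share of time off drug. A reader of that table would take their AE proportions as what happens during short exposure, when part of it happened afterwards.

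**Working it through.** The plan states no AE rate, stopping rate or sample size calculation that bears on this, so there is no figure to reproduce.

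**Step 1: is there any upper bound or separate display?** The two rules in SAP 8.2.1.2 refer only to the start of PRISTIQ. The tables in 8.2.1.3 split by baseline and treatment factors. Those in 8.2.1.4 split by preferred term, severity, action, seriousness, outcome, causality and other cause. SAP 8.2.3 adds blood pressure and the Basic Results tables. None uses onset relative to the last dose.

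**Step 2: how much of the required window is off drug?** For a subject treated for d days (d below 56), the minimum window is d + 28 days and the off-drug share is 28/(d + 28):

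| Days treated | Minimum window | Off-drug share |
|---|---|---|
| 7 | 35 | 80% |
| 14 | 42 | 67% |
| 28 | 56 | 50% |
| 42 | 70 | 40% |
| 55 | 83 | 34% |

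In the under-4-week band d is at most 27, so the share is at least 28/55 = 51%. In the 4-to-under-8-week band it runs from 34% to 50%. These figures need only the 28-day rule and complete follow-up.

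**Step 3: what could this do to the AE proportion in a short band?** The inputs here are assumptions: an eight-week on-drug AE risk p of 10% to 30%, a constant hazard, and an off-drug hazard r times the on-drug one, with r from 0.25 to 1. Then λ = −ln(1 − p)/56. The proportion is 1 − exp(−λd) on drug only, and 1 − exp(−λ(d + 28r)) with the 28 days added. With p = 20%, λ = 0.2231/56 = 0.00398 per day.

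| p | Stop day | On drug only | r = 0.25 | r = 0.5 | r = 1 |
|---|---|---|---|---|---|
| 10% | 14 | 2.6% | 3.9% | 5.1% | 7.6% |
| 20% | 14 | 5.4% | 8.0% | 10.6% | 15.4% |
| 30% | 14 | 8.5% | 12.5% | 16.3% | 23.5% |
| 20% | 42 | 15.4% | 17.7% | 20.0% | 24.3% |

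At p = 20% the proportion is about 1.5 to 2.8 times the on-drug figure for a stop on day 14, and about 1.15 to 1.6 times for a stop on day 42.

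**Step 4: what about the overall incidence?** Take n = 600, p = 20%, a share q stopping on day 14, and everyone else on drug for 56 days.

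- q = 20%: on drug only, 0.2 × 5.4% + 0.8 × 20% = 17.1% (95% CI 14.1% to 20.1%). With the added days it is 17.6% to 19.1%.
- q = 40%: 14.2% on drug only, and 15.2% to 18.2% with the added days.

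The overall shift is therefore 0.5 to 2.0 points at 20% stopping and 1.0 to 4.0 points at 40%, against a confidence interval half-width of about 3 points.

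**The case against.** The strongest reply is that the label does very little. It acts as a filter that admits events after the first dose and leaves out earlier ones. The endpoint in SAP 6.1 is occurrence of AEs, SAP 4 sets no hypotheses, and no later table uses the term. The protocol wants the later events counted. Attribution is a separate step: the psychiatrist rates causality, an unrelated event can be assigned to another treatment or disease, and SAP 8.2.1.4 forms the adverse drug reaction (ADR) tables by the rule "All AEs, except for 'Unlikely', will be considered as AE whose causal relationship to study drug cannot be excluded".

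Most of this stands, and it rules out three stronger readings that a reader might infer.

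- **That the overall AE incidence is wrong.** The documents do not support this. The added events are real AEs that the protocol asks for, so the shifts in step 4 are not bias in the stated endpoint.
- **That withdrawal events contaminate the ADR tables.** A withdrawal reaction is related to the drug and belongs there. An event judged to come from a later treatment leaves those tables if it is rated 'Unlikely'. Unclear cases stay in, and Protocol 7.4.6 records concomitant drugs only while PRISTIQ is given, so a later treatment may be hard to see. That follows from the cautious ADR rule and the CRF, not from the timing label.
- **That 10% to 20% of on-treatment person-time is off drug.** That figure follows if 20% to 40% stop at day 28 on average, since q × 28/56 = q/2. But the SAP labels events, not person-days, and plans no person-time rate.

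The reply does not answer the administration-period comparison, where exposure and events end at different dates, or the lack of any display by timing.

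**Conclusion.** The concern holds in a limited form. The on-treatment class has no end, the protocol requires observation beyond the last dose, and no output separates the later events. Keeping them in the total is right; the label and the missing split are the fault.

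The consequence that reaches a planned result is the comparison by total administration period. For early stoppers, 34% or more of the minimum window is off drug, and over half for those treated under 4 weeks. The effect on AE proportions cannot be fixed from the documents. The range of 8.0% to 15.4% against 5.4% rests on an assumed 20% eight-week risk, a day-14 stop, a constant hazard, and an off-drug hazard of 0.25 to 1 times the on-drug one.

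Protocol 9.2 words its 28 days generally, so longer bands may also hold some post-dose events, but as a smaller share of their follow-up. In a descriptive surveillance study with no comparator this is of moderate severity: a cheap improvement, not a condition for the analysis to be usable.

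**What to change.** In SAP 8.2.1.2:

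1. Keep the all-AE total, but describe it as events with onset from the first dose to the end of the observation or reporting period, and say which of the two is meant.
2. Derive a flag from AE onset date and last PRISTIQ date: onset on or before the last dose, or after it, with no unspecified lag. For subjects still on treatment, use the last date collected, as SAP 8.2.1.1 already does for exposure.
3. State a default for partial dates. For example, class an event as on or before the last dose if its partial date allows that, and footnote the number so classed.

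Then present, for events after the last dose, the AE incidence with its 95% CI and the AE, ADR and SAE counts by preferred term. In SAP 8.2.1.3, repeat the comparison by total administration period using only events with onset up to the last dose, beside the planned version. The repeat puts events and exposure on the same clock. It does not remove the separate difficulty that AEs may themselves cause early stopping.

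The cost is SAP wording, one derived variable, a few extra tables and a default class for partial dates. Onset dates (Protocol 7.4.10.3) and treatment stop dates (Protocol 7.4.5) are already on the CRF, so no new data are needed.
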